#### 2 STUDY OBJECTIVES

- **2.1** Primary Objectives
- 2.1.1 Develop IntelliCare and optimize its functionality through laboratory and field usability testing.
- 2.1.2 Develop the machine learning models and algorithms that will continuously learn from user interactions with IntelliCare to provide intervention recommendations and motivational messaging.
- 2.1.3 Conduct a randomized controlled trial (RCT) comparing 8 weeks of IntelliCare with the machine learning component to 8 weeks of IntelliCare without the machine learning component for the treatment of depression and anxiety. Participants will be evaluated at baseline, week 4, week 8, and at 3- and 6-month post-treatment follow-ups. It is hypothesized that 1) IntelliCare with the recommendations, in contrast to IntelliCare without the recommendations, will produce greater adherence and greater reductions in depressive and anxiety symptoms and 2) IntelliCare with coaching will produce greater greater adherence and greater reductions in depressive and anxiety symptoms. The primary patient centered outcome will be depression/anxiety severity.
- 2.2 Secondary Objectives.
- 2.2.1 Exploration of the mediating effects of adherence markers (e.g. time in treatment, app launches, etc.) coaching variables (e.g. message frequency, timing, etc.), and psychological variables (e.g. change in self-report measures) on depression and anxiety outcomes.
- **2.2.2** Exploration of moderating variables on outcomes, such as baseline demographics, baseline characteristics.
- 2.2.3 Explore, optimize, and validate coaching methods.

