#### PHASE 2: FIELD TRIAL

- 4.1.3 Phase II Field Trial. The purpose of the field trial will be twofold. The field trial will extend usability testing over time and under real life conditions. In addition, the field trial will be used to collect data to develop and evaluate machine learning methods. IntelliCare will be evaluated in up to 200 individuals meeting inclusion criteria in a 8-week, single arm field trial.
- Phase II Enrollment. Participants in the field-trial will be enrolled remotely to avoid excluding 4.1.3.1 participants with access barriers who are among those who would be likely end users. Interested parties will complete a brief telephone or web screen to determine whether there is any reasonable expectation that they might be eligible (data from the brief screen will be included in the study dataset). If they are clearly not eligible they will be informed of this and thanked. If they are eligible they will initiate the consent process. Following the initial pre-consent screening phone call but prior to the eligibility interview, the participant will be emailed a link to the detailed digital version of the consent form. Subjects agree to participate by checking a yes box and typing in their name. They are instructed to print out the consent form for their records. After the study consent form is signed online, detailed information regarding the consent will be reviewed with the participant and witnessing of the consent form will take place at this time by study staff. A date and time for the screening assessment will then be scheduled. An RA will then conduct an eligibility interview with the participant over the phone, where the MINI, HAM-A, and QIDs are administered. Questionnaires will be administered to patients via a secure web based assessment portal, so that the other inclusion and exclusion criteria can be determined. Patients will be paid \$20 for completing the eligibility interview. Payments may be made in either Amazon credits or by check depending on participant preference, NU payment policies, and payment availability at the time of study participation.

If eligible, a research study assistant will work with participants to download the IntelliCare system from the Google Play store. Eligible participants will include those who already own an Android smartphone with an operating system sophisticated enough to support the IntelliCare system (version 4.2.2 or higher).

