- Phase II Assessment, Measures & Compensation. Participants in the field trial will receive telephone-4.1.3.3 based interview evaluations and complete online self-report questionnaires at baseline, week 4 and week 8. All assessments and evaluations will be conducted by an RA who is blind to the treatment (i.e. coaches will not perform assessments on patients they coach). Depression will be measured at baseline by telephone interview using the QIDS-C for severity of symptoms and the MINI MDE module for diagnosis. Self-reported depression will be measured at baseline, wk4 & wk8 using the PHQ-9 administered online. Anxiety will be measured by telephone interview using the HAM-A for severity of symptoms at baseline. Self-reported anxiety will be measured using the GAD-7 administered online at baseline wk4, and wk8. Adherence will be assessed through use data from phone or other platforms (e.g. computer), including number of times the program was accessed, number of times each lesson, tool, and feedback element was accessed and percentage of messages viewed. The first 20 participants will also be engaged in extended usability testing, and will speak with a research assistant weekly, who will inquire into usability problems. We will compensate \$70 to each of the 200 field trial participants for taking part in their follow up assessments (Week 4 and Week 8). Participation in the trial may include the use of texting, and as such, study staff will reimburse participants who do not already have an unlimited monthly texting plan for their upgrade to such. Reimbursement of up to \$30 per month enrolled in the trial (up to two months) is possible. We will not be compensating participants who already subscribe to unlimited texting in their monthly plans. This decision was made in attempt to make the intervention more generalizable, so as not to overincentivize certain users by compensating them for matters already routine to them. Payments may be made in either Amazon credits or by check depending on participant preference. NU payment policies. and payment availability at the time of study participation.

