- 4.4.4 Patient demonstrates disease progression (termination of treatment and follow-up unless continued treatment with study intervention is deemed appropriate at the discretion of the investigator);
- 4.4.5 *Identification of Suicidality.* Suicidality will be monitored at all possible points of contact. It will be monitored by RAs at each assessment point (Field Trial: Baseline, Week 6, and Week 12. RCT: Baseline, Week 6, Week 12, Month 3, Month 6), using the QIDS-C and MINI module(s). Report of an elevated level of suicidal ideation (MINI Suicidality module score of 8 or greater or QIDS question 12 response of 12 score of 2 or greater at baseline; Positive response for MINI MDE section question A3.g or QIDS question 12 score of 2 or greater during later time points) will trigger administration of the CBITS Suicidality Protocol by the RA. Following a structured assessment of suicidal ideation by an RA, the information will be provided to a clinical monitor (Ph.D. level psychologist) who will review the information and take appropriate action (see below). One Ph.D. psychologist will be designated as

clinical monitor at all times. Suicidality will also be monitored in online self-report assessments. A score of 2 or greater on the PHQ-9 item 9 branches to the BDI-I item 9, which assesses for severity of suicidal ideation. Scores of 2 or greater on the BDI-I item 9 will trigger automatic and immediate notification to the RA who will attempt to contact the participant by phone, complete the CBITS Suicidality Protocol with direction and supervision by the Ph.D level clinical monitor as needed. Additionally, Coaches will be trained to identify potential suicidality in the coaching engagement telephone call or secure email communications, which will similarly result in administration of the CBITS Suicidality Protocol.. Information about suicidality will be discussed with the clinical monitor.

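### Section 4.4.5 sets the research assistants' suicidality checks at weeks 6 and 12, but both phases assess at weeks 4 and 8

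*Combined protocol and SAP*

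**What the plan says.** Section 4.4.5 sets the safety rule for suicidality: "It will be monitored by RAs at each assessment point". A parenthesis then lists the points. For the field trial they are baseline, week 6 and week 12. For the randomized trial the text is "RCT: Baseline, Week 6, Week 12, Month 3, Month 6), using the QIDS-C and MINI module(s". At baseline the interview triggers are a MINI Suicidality module score of at least 8 or a QIDS item 12 score of at least 2. After baseline they are "Positive response for MINI MDE section question A3.g or QIDS question 12 score of 2 or greater during later time points". A separate online route applies: "A score of 2 or greater on the PHQ-9 item 9 branches to the BDI-I item 9", and a BDI item 9 score of 2 or more alerts the RA.

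The schedules differ from that list. Section 2.1.3 says of the randomized trial: "Participants will be evaluated at baseline, week 4, week 8, and at 3- and 6-month post-treatment follow-ups"; 4.1.6.1 repeats this. For the field trial, 4.1.3 says "IntelliCare will be evaluated in up to 200 individuals meeting inclusion criteria in a 8-week, single arm field trial", and 4.1.3.3 provides telephone-"based interview evaluations and complete online self-report questionnaires at baseline, week 4 and week 8".

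On instruments, 4.1.3.1 describes a field-trial eligibility interview "where the MINI, HAM-A, and QIDs are administered", and 4.1.3.3 places the QIDS-C and the MINI MDE module at baseline. For the randomized trial, 4.1.5.3 and 4.1.6.1 name the MINI at baseline and do not mention the QIDS-C. Section 6.11.1 nevertheless lists QIDS-C and MDD among the RCT outcomes to be modelled longitudinally.

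**The concern.** This is an operative safety instruction, and it gives staff two answers to when the RA check is due. The general rule points to weeks 4 and 8. The list points to weeks 6 and 12, when neither phase has an assessment.

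The RA check is not a duplicate of the online route. Online, a participant must score at least 2 on PHQ-9 item 9 and then at least 2 on BDI item 9 before anyone is alerted, so a PHQ-9 item 9 score of 1 never branches. The post-baseline MINI trigger is a single positive answer. Participants with lesser suicidality can enrol, because exclusion 3.2.3 requires ideation, plan and intent together. Half of the RCT participants have no coach who might notice a problem.

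What is at stake is therefore the timing of the RA check and its link to the planned interviews. The trial's estimates and tests are not affected.

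**Working it through.** The plan states no figure to reproduce here, so the check sets the sections side by side.

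**Step 1: time points.** Inputs are the list in 4.4.5 and the schedules in 2.1.3, 4.1.3.3 and 4.1.6.1.

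| Phase | Listed in 4.4.5 | Scheduled assessments | Listed and scheduled | Listed, not scheduled | Scheduled, not listed |
|---|---|---|---|---|---|
| Field trial | baseline, wk 6, wk 12 | baseline, wk 4, wk 8 | 1 | 2 | 2 |
| RCT | baseline, wk 6, wk 12, mo 3, mo 6 | baseline, wk 4, wk 8, mo 3, mo 6 | 3 | 2 | 2 |
| Total | 8 points | 8 points | 4 | 4 | 4 |

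So 4 of 8 listed points match no assessment. After baseline the figure is 4 of 6 (2 of 2 in the field trial, 2 of 4 in the RCT). Week 12 falls 12 − 8 = 4 weeks after treatment ends.

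This count takes months 3 and 6 in 4.4.5 as post-treatment, as in 4.1.6.1. If they ran from baseline, 6 of 8 would be unmatched. That reading is unlikely: month 3 would fall at about week 13, one week after the listed week 12.

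**Step 2: which schedule is current.** The payments follow weeks 4 and 8. Section 4.1.3.3 compensates follow-up at those weeks. In 4.1.6.1, $40 + 2 × $30 (weeks 4 and 8) + 2 × $30 (months 3 and 6) = $160, the stated maximum. Section 6.9.2 still uses a 12-week intervention for power, which suggests that weeks 6 and 12 survive from a longer design. That is an inference.

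**Step 3: instruments.** The comparison is between the 4.4.5 triggers and the interview measures named in the screening and assessment sections.

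- Field trial, baseline: MINI and QIDS are both named. The triggers are supported.
- RCT, baseline: the MINI is named and the QIDS-C is not. The triggers are alternatives, so the MINI is enough, assuming that the MINI interview includes its suicidality module.
- After baseline, both phases: telephone interviews are planned, but 4.1.3.3 and 4.1.6.1 name no interview measure for them. The depression and anxiety measures named at those times are the online PHQ-9 and GAD-7.

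**Step 4: what still operates.** The PHQ-9 is given online at every scheduled assessment, so the online alert is available at each. Section 4.4.7 requires an RA who sees substantial deterioration to inform the clinical monitor. Coaches are trained to detect suicidality. Section 4.1.3.2 gives every field-trial participant a coach, and in the RCT groups 1 and 3 have one (75 + 75 = 150 of 300).

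**The case against.** The strongest reply is that the rule itself is sound. It requires a check at every assessment and opens by asking for monitoring whenever contact allows; the weeks are only a gloss in parentheses. A sensible team would check at weeks 4 and 8, and on that reading there is no timing gap. This stands as a limit on the consequences. It does not remove the error, because the gloss gives specific weeks that contradict every schedule in the document.

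On instruments, the reply is that 4.4.5 itself assigns the QIDS-C and MINI items to the RA check, and that outcome sections need not repeat safety items. This also stands. Sections 4.1.3.3 and 4.1.6.1 do not say that these interviews are given at baseline only, and 6.11.1 implies that the QIDS-C may be repeated in the RCT, although that too may be older text. The gap is one of cross-reference, not a contradiction.

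A reader might go further and infer that RCT participants have no RA check until about week 21 (8 + 13 weeks), the first listed post-baseline point that coincides with an assessment, and that the field trial has none after baseline. The documents do not support this. It requires setting aside both the every-assessment rule and the week 6 and 12 checks that the list demands. Multiplying the mismatch by enrolment adds no information. Nor can one infer that the later triggers can never fire.

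**Conclusion.** The timing conflict is real, and nothing elsewhere in the document corrects it: 4 of the 8 time points listed in 4.4.5 match no scheduled assessment, and weeks 4 and 8 are missing from the list in both phases. The count rests on reading months 3 and 6 as post-treatment.

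The instrument point is secondary. After baseline, the interview triggers are not linked to a named interview measure in either phase, and in the RCT the status of the QIDS-C is unclear because 4.4.5 and 6.11.1 refer to it while the screening and assessment sections do not.

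Suicidality monitoring remains in place by several routes. The documents do not show that any participant would go unmonitored, and the primary analysis is untouched. The correction should be made because the text is a safety instruction and the change is nearly free.

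**What to change.** In 4.4.5, replace weeks 6 and 12 with weeks 4 and 8 for both phases, and state that months 3 and 6 in the RCT are counted from the end of treatment. In 4.1.3.3 and 4.1.6.1, add that the RA asks the 4.4.5 suicidality item(s) in the telephone interview at each post-baseline assessment.

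Keep both alternative triggers wherever both instruments are given; cutting them to one would narrow the safety net without need. For the RCT, either schedule the QIDS-C item or state that the MINI item is the operative trigger. Leave the online route unchanged.

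The cost is a protocol amendment and one or two items in the RA script for the telephone interviews. Section 4.1.3.3 already places those interviews at weeks 4 and 8. Section 4.1.6.1 says that assessments include telephone interviews without naming the visits, so the amendment should confirm that each RCT visit has one. If the field trial is already complete, only the RCT changes have practical effect.

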# PHASE 3 RANDOMIZED CONTROLLED TRIAL

- 4.1.4 Phase III Randomized Controlled Trial. For the RCT, 300 participants meeting entry criteria will be enrolled over 13 months (approximately 23 per month). Participants will be randomized using a factorial design with the following factors:
- **4.1.4.1** Factor 1. Hub App with intelligent recommender system/Hub app without intelligent recommender system: This factor is consistent with Objective 2.1.3 on pg. 4
- **4.1.4.2** Factor 2. Coaching/No Coaching: This factor would allow us to examine and control for the effect of coaching.
- **4.1.5** *Phase III Enrollment.* Participants in the RCT will be enrolled remotely to avoid excluding individuals with access barriers who are among those who would be likely end users. Screening will be conducted in 3 stages.
- 4.1.5.1 Screening Stage 1 (pre-consent): Interested parties will complete a brief web screen to determine whether there is any reasonable expectation that they might be eligible (data from the brief screen will be included in the study dataset). If they are clearly not eligible they will be informed of this and thanked. If they appear to be eligible a research assistant will follow-up by phone to clarify responses from the web screen and ask additional phone screening questions. If the participant passes the stage 1 phone screen s/he will be invited to initiate the online consent process and proceed to screening stage 2 described below.

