- **4.1.5.4** Study Enrollment: A research study assistant will work with participants to download the IntelliCare apps from the Google Play store, and if assigned to work with a coach, schedule the coach orientation call.
- **4.1.6** *Phase III Treatment Plan.* The IntelliCare intervention will be comprised of a combination of 3 components: (1) IntelliCare Treatment Apps, (2) IntelliCare Hub App, (3) and Coaching. A brief description of each component appears below.
  - 1. IntelliCare Treatment apps: There are 13 IntelliCare treatment apps. Each app instantiates a single behavioral strategy (e.g. scheduling positive behaviors, thought restructuring, goal setting, etc.), and takes only a few seconds to use. The apps address specific treatment goals, and may include didactic content as well as interactional components (e.g. activity scheduling/monitoring, thought records, etc.) that support behavior change. All participants will download the apps onto their own phones and use them daily during the 8 week intervention period.
  - 2. IntelliCare Hub app: The "Hub" app integrates the treatment apps and organizes the user's experience. We will be testing two different versions of the hub app; one with an intelligent recommender system (version A) and one without (version B). The recommender system in version A will use machine learning, which can learn from a patient's interactions with the intervention, to deliver and adapt treatment to the needs and preferences of the participant.
  - 3. Coaching: BA level coaches (supervised by a licensed psychologist), may support participants throughout the 8 week intervention period. We have developed a low-intensity coaching model that relies primarily on brief text messaging to promote engagement, along with one engagement orientation call at the beginning of treatment, and the option of a second call if needed.

While **all** participants will have access to the treatment apps during the 8-week intervention period, the version of the Hub app and the inclusion of coaching will vary for each participant according to random assignment to one of 4 groups:

```
Group 1 (n=75): Hub App Version A + Treatment Apps + Coaching
```

Group 2 (n=75): Hub App Version A + Treatment Apps + Independent Use (no coaching)

Group 3 (n=75): Hub App Version B + Treatment Apps + Coaching

Group 4 (n=75): Hub App Version B + Treatment Apps + Independent Use (no coaching)

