At the end of the 8 week intervention, all participants will be informed that they may continue using the IntelliCare system on their phones but participants in groups 1 and 3 will no longer have access to their coach. For any participants who do continue app use after the study period has ended, the IntelliCare system will continue to collect app data as before.

4.1.6.1 Phase III Assessment, measures and compensation. RCT participants will receive trial assessments at baseline, week 4, and week 8 (post-treatment). Post-treatment follow-up evaluations will occur at 3 and 6 months to evaluate maintenance of gains. Assessments will consist of telephone based interviews and online self-report questionnaires. All assessments and evaluations will be conducted by an RA (i.e. coaches will not perform assessments on patients they coach). Depression will be measured at baseline by telephone interview using the MINI MDE module. Self-reported depression will be measured at baseline, wk4, wk8, 3 months post-treatment and 6 months post-treatment using the PHQ-9 administered online. Self-reported anxiety will be measured using the GAD-7 administered online at

baseline wk4, wk8, 3 months post-treatment and 6 months post-treatment. *Adherence* will be assessed through app use data from phone, including number of times the apps were accessed, number of times each app feature was accessed and percentage of messages viewed. Participants will be paid up to \$40 for the screening/baseline assessments, \$30 for the week 4 and 8 assessments, and \$30 for the 3 and 6 month assessments (total= up to \$160). Participants will not be compensated for using the apps or communicating with the study coach. Payments may be made in either Amazon credits or by check depending on participant preference, NU payment policies, and payment availability at the time of study participation. Individuals recruited through Focus Pointe Global will be paid through PayPal by Focus Pointe Global.

**4.1.7** *Phase II Study Retention.* Communication from the research study may occur across a participant's involvement in the trial to increase participant retention. Such contact could include sending greeting cards via mail or email (thank you, birthday, etc.) or sending small tokens of appreciation (keychains, pens, stress balls).

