- Ensuring patient safety. Once the monitor (or any study clinician, who will serve as the monitor) is 4.4.6 notified of potential suicidality, the monitor will take all actions necessary to ensure patient safety. This includes: evaluation of all necessary data including study records, calling the patient for further evaluation, recommending hospitalization, calling emergency services in the participant's jurisdiction to perform a "health and safety" check, or any other actions deemed necessary to ensure the safety of the patient. The monitoring clinician also has the option of recommending that the patient be discontinued from the study and referred for more appropriate care. Because RAs are usually the main point of contact for patients, they will be given thorough training in the assessment of suicidality. While the clinical monitors will be responsible for the management of suicidal patients, it is possible that an emergent situation will arise that requires immediate attention. RAs (assessors and coaches) will be trained in the use of the CBITS Suicidality Protocol. This document includes a well-validated measure for assessing suicidal risk (Columbia Suicide Severity Rating Scale) and structured follow-up steps based on the participants' reported score. RA's will also standardly collect information regarding participants' current location when contacting the participant by phone in the case there is a need to contact emergency services. The PI will also be notified of all cases of suspected suicidality, will consult with the clinical monitor, and will be continuously updated. Any psychiatric problem rising to the level of an adverse event will be reported to the IRB and to the DSMB chair.

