- 4.4.7 Patient Deterioration. Clinical deterioration as evidenced by an increase in the severity of depressive or psychiatric symptoms is the other potential risk. If the RA believes that a participant has deteriorated substantially either by showing a worsening in the presenting psychiatric symptoms or by the development of new psychiatric or treatment related symptoms, the clinical monitor will immediately be informed. The clinical monitor will evaluate the participant, notify the PI and DSMB, and make any necessary referrals for the care of the participant. If the PI, in consultation with the DSMB, determines it is in the participant's best interest to cease participation in the study, the patient will be terminated from the study, and referrals and assistance will be given in obtaining appropriate treatment. Reports will be filed with all necessary governing bodies, including the Northwestern University IRB and the DSMB.
- **4.4.8** Treating physician judges continuation on the study would not be in the patient's best interest;
- 4.4.9 Lost to follow-up. If a research subject cannot be located to document survival after a period of 2 years, the subject may be considered "lost to follow-up." All attempts to contact the subject during the two years must be documented and approved by the Data Monitoring Committee.
- 5 Adverse Event Monitoring
- 5.1.1 Adverse event data collection and reporting, which are required as part of every clinical trial, are done to ensure the safety of Subjects enrolled in the studies as well as those who will enroll in future studies using similar agents. Adverse events are reported in a routine manner at scheduled times during a trial. Additionally, certain adverse events must be reported in an expedited manner to allow for optimal

- monitoring of patient safety and care.
- 5.1.2 All patients experiencing an adverse event, regardless of its relationship to study drug/device, will be monitored until:
- 5.1.2.1 the adverse event resolves or the symptoms or signs that constitute the adverse event return to baseline;
- **5.1.2.2** any abnormal assessment ratings/observations have returned to baseline;
- 5.1.2.3 there is a satisfactory explanation other than the study intervention for the changes observed; or
- **5.1.2.4** death.

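### Coached groups have an extra human route for detecting suicidality, and no adverse event enquiry common to all four groups is described, so safety counts by coaching may reflect detection rather than risk

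*Combined protocol and SAP*

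**What the plan says.** **Randomised coaching.** Under Phase 3, "For the RCT, 300 participants meeting entry criteria will be enrolled over 13 months" in a factorial design in which coaching is one factor. Section 4.1.6 lists the two uncoached arms as "Group 2 (n=75): Hub App Version A + Treatment Apps + Independent Use (no coaching") and "Group 4 (n=75): Hub App Version B + Treatment Apps + Independent Use (no coaching"). Groups 1 and 3, also 75 each, have a coach. Coach access ends after the 8-week intervention.

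**Routes stated for everyone (4.4.5).** Research assistants (RAs) monitor suicidality at each assessment point, given as "RCT: Baseline, Week 6, Week 12, Month 3, Month 6), using the QIDS-C and MINI module(s"). In the online questionnaires, a score of 2 or more on PHQ-9 item 9 leads to BDI-I item 9, and a score of 2 or more there alerts the RA automatically. Under 4.1.6.1 depression is followed to 6 months after treatment "using the PHQ-9 administered online", with the GAD-7 at the same times.

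**Route that needs a coach (4.4.5).** "Coaches will be trained to identify potential suicidality in the coaching engagement telephone call or secure email communications", and this starts the same suicidality protocol. Section 4.4.6 adds that "RAs (assessors and coaches) will be trained in the use of the CBITS Suicidality Protocol".

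**Deterioration (4.4.7).** The trigger is worded "If the RA believes that a participant has deteriorated substantially". The clinical monitor then evaluates the participant. Ending participation is for the principal investigator to decide in consultation with the DSMB.

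**Adverse events (section 5).** Events are defined, graded, attributed and reported, with routine reporting at scheduled times. No question, checklist or visit for eliciting them is named. Section 6 plans no comparison of adverse events or suicidality between groups.

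**The concern.** A safety count compares randomised groups fairly only if events are looked for in the same way in each group. Here one means of looking is tied to a randomised factor. A coach exchanging messages for 8 weeks can learn of suicidal thoughts, an emergency visit or a hospital stay between assessments. In the uncoached groups such an event waits for the next assessment, and if nobody asks about it there, it depends on the participant volunteering it.

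What a coach learns does enter the record. Coach notes are listed as study data in 4.3. Under 4.4.6 the principal investigator is told of all suspected suicidality, and psychiatric adverse events go to the IRB and the DSMB chair.

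The coaching effect is a stated hypothesis in 2.1.3, so readers will look at safety by coaching even without a formal test. If the counts differ, the present record would not show whether risk or detection was the cause.

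**Working it through.** **1. Who has the extra route.** Uncoached = 75 + 75 = 150; 150/300 = 50%. The route lasts 8 weeks. After week 8 no group has a coach, so the longer gaps during follow-up affect all groups alike.

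**2. What is searched for, and in whom (RCT, after baseline).**

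| Harm | Route in all four groups | Extra route in Groups 1 and 3 |
|---|---|---|
| Suicidality | RA monitoring; PHQ-9 item 9, then BDI-I item 9 with alert | Coach call and messages (4.4.5) |
| Symptom worsening | PHQ-9, GAD-7, RA judgement | Possible, if coaches count as RAs (inferred from 4.4.6) |
| Other events, e.g. hospitalisation | None described | Informal, through coach contact |

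The imbalance therefore concerns suicidality between assessments and adverse events in general.

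**3. How firm the common RA route is.** Section 4.4.5 places it at weeks 6 and 12 with the QIDS-C and MINI. Section 4.1.6.1 has assessments at weeks 4 and 8, names the MINI MDE module at baseline only, and does not list the QIDS-C. It does say that assessments include telephone interviews, but names no interview instrument after baseline. The two sections cannot both describe the same schedule. If 4.1.6.1 governs, the PHQ-9 item 9 branch is the only common post-baseline suicidality screen specified. If 4.4.5 governs, the coach route is still additional.

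**4. Possible size.** The plan has no figure to reproduce, and every input here is an assumption. Let the common routes detect a share d of events, and a coach detect a share c of those missed. With equal true risk, the ratio of recorded events (coached/uncoached) is

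R = [d + (1 − d)c] / d.

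| d | c | R |
|---|---|---|
| 0.9 | 0.2 | 0.92/0.9 = 1.02 |
| 0.7 | 0.5 | 0.85/0.7 = 1.21 |
| 0.6 | 0.3 | 0.72/0.6 = 1.20 |
| 0.5 | 0.5 | 0.75/0.5 = 1.50 |
| 0.3 | 0.3 | 0.51/0.3 = 1.70 |
| 0.3 | 0.5 | 0.65/0.3 = 2.17 |

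As counts, at an assumed true risk of 10% with 150 per side: 150 × 0.10 × 0.92 = 13.8 against 150 × 0.10 × 0.9 = 13.5 in the first row, and 150 × 0.10 × 0.75 = 11.25 against 150 × 0.10 × 0.5 = 7.5 in the fourth.

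**5. Could detection alone produce a significant difference?** Let p1 and p2 be the recorded proportions in the uncoached and coached groups. By the normal approximation, the chance of two-sided p < 0.05 in the direction of more events with coaching is Φ[(p2 − p1 − 1.96·SE0)/SE1], where SE0 and SE1 are the pooled and unpooled standard errors. For true risk of 5–20%, d of 0.5–0.9 and c of 0.2–0.5 it runs from about 3% to 26%. The upper end is at 20% risk with d = c = 0.5: p1 = 0.10, p2 = 0.15, SE0 = 0.0382, SE1 = 0.0381, giving Φ(−0.65) = 0.26. With no artefact the figure would be 2.5%.

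**6. Opposite direction.** Over the assumptions in step 5, a true risk ratio for coaching of 1/1.50 = 0.67 to 1/1.02 = 0.98 would exactly offset the extra detection. The artefact could therefore also hide a benefit.

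**The case against.** The strongest reply is that the two harms of most concern, suicidality and worsening symptoms, are screened in all four groups, that the asymmetry follows from randomising human contact, that it lasts 8 weeks, and that no planned test uses adverse event counts. All of that stands. It limits the point to reporting and interpretation and leaves the efficacy tests as planned.

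A reader might infer more than the documents support:

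- **That uncoached participants are followed only by an online questionnaire item.** Section 4.4.5 gives RA monitoring without restriction by group, and the online alert fires on BDI-I item 9 after PHQ-9 item 9.
- **That no assessment asks about adverse events at all.** Section 4.3 points to a Measures Appendix for the full list of self-report measures, and that appendix is not in the supplied text. What can be said is that the text describes no such enquiry.
- **That coaches will cause uneven removals.** The coach route to 4.4.7 is inferred from a parenthesis in 4.4.6 about training, and ending participation needs a decision by the principal investigator with the DSMB.
- **That coaching will look less safe, or that the DSMB will be misled.** Coaching may lower true risk, which works against the artefact, and the DSMB contacts in 4.4.6 and 4.4.7 concern individual cases.

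A further fair objection concerns the remedy. Restricting safety tables to events found by questionnaire would lose deaths and events in people who stop responding, and coaching might itself affect completion. The fix below therefore keeps all events in view.

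**Conclusion.** The point holds in limited form. Half the RCT has an additional human detection route for suicidality during 8 weeks, tied to a randomised factor, and the supplied text describes no adverse event enquiry common to all groups. Counts of adverse events and suicidality by coaching may therefore differ through detection alone, mainly between assessments and for events other than suicidality and symptom change.

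The size is unknown. Ratios from about 1.0 to 2.2 follow from assumed detection shares (common routes 30–90%, coach 20–50% of what is missed) and equal true risk; none of these comes from the documents. The lower end applies if the common screening works well, which makes the conflict between 4.4.5 and 4.1.6.1 important. The part about general adverse events weakens if the Measures Appendix already contains such items; the coach asymmetry for suicidality remains either way. The change is worth making because it is cheap and cannot be made after the data are collected.

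**What to change.** 1. Unless the Measures Appendix already has one, add the same short adverse event block (hospital or emergency care, self-harm, any other new health event since the last assessment) to the online questionnaires at weeks 4 and 8 and at the 3- and 6-month follow-ups, in all four groups.
2. Record the source of detection for every event: scheduled assessment, coach, spontaneous or other.
3. Report all events by group and source. Show the coaching comparison on events from the scheduled common source alongside the total, with deaths and other serious events always included.
4. Continue to act on events that coaches detect. The change concerns recording and tabulation only.
5. Reconcile 4.4.5 with 4.1.6.1 on assessment times and instruments, and state whether RA in 4.4.7 includes coaches.

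The cost is a few questionnaire items and one data field. The downsides are slightly longer questionnaires and more self-reported events to review.
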